## 1.2. Objectives of Statistical Analysis

### ***Primary:***

- To assess the treatment effect of FX006 on pain following an intra-articular (IA) injection in patients with hip osteoarthritis (OA)

### ***Secondary:***

- To assess the efficacy of FX006 on function, global impression of change, stiffness, quality of life, treatment satisfaction, sleep quality and consumption of rescue medication in patients with hip OA
- To assess the safety of FX006 in patients with hip OA

This statistical analysis plan (SAP) is designed to outline the methods to be used in the analysis of study data in order to answer the study objective(s). Populations for analysis, data handling rules, statistical methods, and formats for data presentation are provided. The statistical analyses and summary tabulations described in this SAP will provide the basis for the Part I results sections of the clinical study report (CSR) for this trial, as well as used for regulatory filings and manuscripts and presentations.

This SAP will also outline any differences in the currently planned analytical objectives relative to those planned in the study protocol.

---

## 2. STUDY DESIGN

### 2.1. Synopsis of Study Design and Randomization Methodology

This is a two-part, multi-center, randomized, double-blind, placebo-controlled, parallel-group study in patients with hip OA. Approximately 70 patients will be enrolled in Part I and approximately 440 patients will be enrolled in Part II of the study. In each part, patients will be randomized to one of two treatment groups (1:1) and treated with a single IA injection of either 32 mg FX006 or normal saline.

Eligible patients will be randomized within strata defined by Baseline Western Ontario and McMaster Universities Osteoarthritis Index (WOMAC) A (pain) (0-10 numeric ratings scale (NRS)) average of Screening 2 and Day 1 with the following classifications: 5.0 to < 6.0, 6.0 to < 7.0, and ≥ 7.0 to 9.0.

FX006 or saline placebo will be administered as a single IA injection with a 12-week follow-up period in the double-blind phase.

Patients participating in Part I of the study will be treated with a single IA injection of either 32 mg FX006 or normal saline and will return for follow up visits at Weeks 12, 16, 20, and 24 or up until implementation of Protocol Version 3.0. The patients will be discontinued at the time of notification by the Investigator.

### 2.2. Stopping Rules and Unblinding

If there is a clinical adverse event (AE) that the Investigator judges requiring unblinding of study medication, they will promptly contact the Medical Monitor and review the situation. If the consensus is to unblind the subject's treatment, a trained and authorized site user will log into the Emergency Study Code Break Module and will be provided the patient's treatment assignment.

If there is a clinical AE that Pharmacovigilance or Regulatory judge requires unblinding of study medication, the Sponsor's internal procedure will be followed.

If any site team member is unblinded for any reason, the Investigator will notify the Sponsor that unblinding has occurred, without revealing the treatment, and document who was unblinded, the reason for doing so, and the date of unblinding in a note to file.

There will be no data review committee for this study.

Furthermore, discontinuation from treatment is not applicable to this study as each randomized patient in the Part I and the Part II double blind phase of the study receives study medication at a single administration.

### 2.3. Study Procedures

Patients participating in this study will complete visit schedules and procedures as detailed in the Schedule of Study Assessments ([Table 1](#)).

**Table 1 Schedule of Study Assessments for Double Blind Phase**

List of Assessments	Screening a Day -30 to -1	Screening 2 a Day -10 to -4	Day 1	Weeks 1, 4, 8 m	Week 12 EOS for Double blind phase a, m
Informed consent	X				
Inclusion/Exclusion Review	X		X b		
Medical History/Update	X		X b		
Patient Demographics	X				
OA Medical History	X				
Prior Treatments and Medications	X		X b		
Physical examination	X				X
Index Hip Assessment	X		X b	X	X
Index Hip X-ray c	X				X
Vital signs	X		X b	X	X
Height	X				
Weight and BMI	X				X
Hematology, Chemistry h	X				X
ESR	X				
HIV, Hep B/C h	X				
Pregnancy Test f	X h		X b		X
Washout of restricted pain medication	X d				
PD-Q, PHQ-9, GAD-7, PCS, ISI	X				
Randomization			X b		
Second Injection Criteria					X
Index Hip Aspiration			X b, g		
IMP administration i			X		
Rescue Medication dispensing and accountability e	X		X	X	X
Accurate pain reporting and placebo response reduction training j		X	X b	X	X
WOMAC k		X	X b	X	X
PGIC k				X	X
TSQM-9 k					X
SI, HOOS-QOL, EQ-5D-5L k			X b	X	X
AE/SAE & ConMeds l				-----X-----	

- a. The Double-Blind Phase of the study ends at Week 12. Patients participating in Part I of the study will not receive a second injection but will return to the clinic at Weeks 12, 16, 20, and 24 or up until the time of this amendment. Patients participating in Part II of the study who are eligible for the second injection in the open-label phase at Week 12 will receive an open-label injection of FX006 at Week 12 and return for follow-up visits at Weeks 16, 20, and 24. These patients will complete the study at Week 24. Patients participating in Part II of the study who are not clinically indicated for a second injection at Week 12 will return to the clinic at Weeks 16, 20, and 24 and will receive an open-label injection of FX006 at the first evaluation where the patient has been determined to meet all criteria.
- b. To be collected or assessed prior to injection of study medication
- c. X-ray of weight-bearing anterior-posterior view for index hip will be taken for central reading.
- d. After signing the ICF, patients must stop all restricted medications (other than rescue medication). The washout (at least 5 half-lives) must be completed at least 2 days prior to Screening 2 visit.
- e. Rescue medication will be dispensed to the patient at the Screening visit, and a new bottle will be dispensed at each subsequent visit as needed. Drug accountability will be done at each visit
- f. Pregnancy tests will be done in women of child bearing potential. *Serum Pregnancy Test* to be collected only at Screening visit. *Urine Pregnancy Test* to be collected prior to injection of study medication and at EOS (when it occurs)
- g. Aspiration must be attempted prior to all injections. If effusion is detected by fluoroscopy guidance, withdraw to near dryness prior to injection
- h. Via Central Laboratory
- i. To be performed under fluoroscopy guidance
- j. To be completed prior to questionnaires
- k. To be completed after APR and PRR training but prior to any other assessments.

- 
1. AEs and concomitant medications will be captured from Day 1 (post injection) to EOS visit.
  - m. Visit should be conducted within +/- 3 days from scheduled date.
  - n. Screening 1 and Screening 2 visits can be combined into one visit provided the patient does not have a washout from prohibited medications. If there is no washout, please perform APR/PRR first, then the questionnaires, with the WOMAC being completed after APR/PRR, then all subsequent questionnaires as they are listed for Screening 1.

## 2.4. Efficacy and Safety Endpoints

All endpoints will be exploratory in Part I of the study. The primary comparison for the primary endpoint will be FX006 32 mg versus placebo.

### 2.4.1. Primary Efficacy Endpoint

- Change from Baseline on the WOMAC A (pain) score at Week 12

### 2.4.2. Key Secondary Efficacy Endpoints

- Change from Baseline on the WOMAC C (function) score at Week 12
- Patients' Global Impression of Change (PGIC) score at Week 12

#### 2.4.2.1. Additional Secondary Efficacy Endpoints

- Area Under the Effect curve (AUE) of change from Baseline on the WOMAC A (pain) subscale over the time intervals (e.g., Weeks 1 to 4, Weeks 1 to 8 and Weeks 1 to 12)
- AUE of change from Baseline on the WOMAC C (function) score over the time intervals (e.g., Weeks 1 to 4, Weeks 1 to 8 and Weeks 1 to 12)
- PGIC at Weeks 1, 4 and 8
- Change from Baseline on the WOMAC A (pain) score at Weeks 1, 4, and 8
- Change from Baseline on the WOMAC C (function) score at Weeks 1, 4, and 8
- Change from Baseline on the WOMAC B (stiffness) score at Weeks 1, 4, 8, and 12
- Change from Baseline on the WOMAC total score at Weeks 1, 4, 8, and 12
- Percent of responders (defined as patients with high improvement in pain or function) according to Outcome Measures in Rheumatology OARSI (OMERACT-OARSI) criteria at Weeks 1, 4, 8, and 12
- Proportion of patients experiencing a  $\geq 20\%$ ,  $\geq 30\%$ , or  $\geq 50\%$  decrease in WOMAC A (pain) at Weeks 1, 4, 8, and 12
- Rescue medication use at Weeks 1, 4, 8, 12 and total consumption
- Change from Baseline on the SI at Weeks 1, 4, 8, and 12

- 
- Change from Baseline on the EuroQol (EQ) 5 Dimensions 5 Levels questionnaire (EQ-5D-5L) at Weeks 1, 4, 8, and 12
  - Change from Baseline on the Hip Injury and Osteoarthritis Outcome Score – Quality of Life Subscale (HOOS-QOL) at Weeks 1, 4, 8, and 12
  - TSQM-9 at Week 12
  - Change from Baseline on WOMAC A (pain), B (stiffness), C (function) and PGIC at Weeks 1, 4, 8, and 12 in patients with unilateral hip OA

---

### 3. PATIENT POPULATIONS

#### 3.1. Population Definitions

The following patient populations will be used for presentation and analysis of the data:

- Full Analysis Set (FAS) Population: All patients who received a full dose of study drug. The FAS Population will be used to examine efficacy endpoints for the double-blind phase of the study. This population will be analyzed as randomized.
- Safety Population (SP): All subjects who received at least one dose (full or partial) of study drug. The Safety Population will be used to assess safety and tolerability. This population will be analyzed as treated.

One Part I patient received a second dose under a previous version of the protocol. This patient's data will be included in the SP in its entirety, but only data prior to the second dose will be used in the FAS.

---

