5.2.8. Rationale for Protocol Amendment

In contrast with the prior experience injecting FX006 into the knee joint, there have been occurrences of incomplete administration of FX006 variously reported as "increased resistance" or "blockage" encountered during the injection of FX006 into the hip joint. Careful review of the cases failed to identify a common factor and initial laboratory studies were inconclusive.

Therefore, screening and enrollment for the FX006-2018-015 study was suspended by the Sponsor to allow for additional review of these cases of incomplete administration of FX006 and further investigation. Repeat administration of FX006 for qualifying patients in the OLE Phase was also suspended.

As part of the investigation to determine the root cause for these incomplete administrations, a laboratory model was developed to explore factors that could contribute to these events. The laboratory model identified two procedural factors potentially contributing to these incomplete administrations of FX006 into the hip joint. Specifically, if a syringe of resuspended FX006 was attached directly to a vertically placed spinal needle (as typically encountered during IA injection in the hip) and outflow from the needle was mildly restricted by the laboratory model simulating constrained joint space conditions, then blockage was observed at an appreciable rate. If the syringe was held horizontally or if the constrained joint space model was omitted (giving conditions similar to IA injection in the knee), such events did not occur.

Based on these findings, the FX006-2019-017 study was implemented to determine the feasibility of administering FX006 into the hip joint using a technique(s) based upon the laboratory findings.

Due to the duration of the enrollment and dosing hold, and the restriction that patients enrolled were not able to receive an open-label administration of FX006 per protocol, this amended protocol was created to separate this patient population impacted by the study hold (Part I). Per this amendment, patients enrolled up to that time were followed for at least 12 weeks or up to the time of this amendment. At the time that this amendment is implemented, patients are to be discontinued from the study without further assessments required.

The outcome of the FX006-2019-017 study will inform future modifications to this protocol.

CONFIDENTIAL Page 27 of 72

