7.5.11. Treatment Compliance

Study medication will be administered by the unblinded injector in the clinic. Details regarding study medication administration will be documented in the electronic Case Report Form (eCRF). The receipt, dispensation and return/destruction of any study medication will be properly documented.

If for any reason the administration of study medication is stopped before the entire volume is injected, the injector should document the reason for stopping administration.

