9.2.1. Analysis Populations

The following analysis populations are planned for each part of this study as follows:

- Full Analysis Set (FAS) Population: All patients who received study drug. The FAS population will be used to examine efficacy endpoints for the double-blind phase of the study
- Safety Population: All subjects who received at least one dose of study drug. The Safety Population will be used to assess safety and tolerability
- Second Injection Population (Part II only): All patients who received a second injection. The Second Injection Population will be used to examine efficacy endpoints in the openlabel extension phase of the study
- Per Protocol Population (Part II Only): All patients in the FAS population who completed the Week 12 visit with no major protocol deviations that may impact the evaluation of the primary efficacy endpoint based on blinded data prior to unblinding of the double-blind phase data.

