#### **4.2.7. Discontinuations and Loss to Follow-up**

Each treated patient from this study receives study medication as a single IA injection. Therefore, discontinuation from treatment is not applicable.

Each patient may only discontinue from the study for further assessments and study visits. Data collected from discontinued patients will be included in the CSR. Patients who discontinue from the study may be replaced at the discretion of the sponsor. Version 3.0 of the protocol separated the study into two parts as the study was put on-hold to new recruitment for an extended period to investigate six patients that did not receive complete study drug administration. All patients enrolled up to the time that the amendment was implemented at each site were followed for at least 12 weeks or up to the time of this amendment, when they were discontinued from the study.

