## 4.10. Efficacy Evaluation

All efficacy analyses will be conducted using the FAS.

In addition to the analyses described below, subgroup analyses will be performed as described in [Section 4.2.6](#).

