## 5. CHANGES TO PLANNED ANALYSES

There are no major changes to the planned analyses.

The following minor changes were made:

1. As a result of the six patients who were unable to receive complete study drug administration, the analysis populations were updated as follows:
  - a. The FAS was updated to clarify that this includes only patients who received a full dose of study drug ([Section 3.1](#)).
  - b. The SP was updated to clarify that this includes all patients who received at least one dose (full or partial) of study drug ([Section 3.1](#)).
2. Study site was added as a covariate, since it was determined in previous studies to be an important covariate ([Section 4.2.4](#)).
3. The protocol indicates that categorical end points will be compared via chi-square or exact tests. Instead, logistic regression will be used to analyze the WOMAC A pain ([Section 4.10.1.3](#)), PGIC categorical ([Section 4.10.2.2](#)) and OMERACT responder ([Section 4.10.3](#)) outcomes. This allows us to control for covariates in the models.

---

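### The SAP narrows the Full Analysis Set to full-dose recipients, contrary to the protocol, and plans no all-treated efficacy analysis for Part I

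*SAP*

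**What the plan says.** Protocol 9.2.1 defines the efficacy set for each part of the study as "Full Analysis Set (FAS) Population: All patients who received study drug". The protocol synopsis adds a Baseline and at least one post-dose pain evaluation, but it also has no full-dose condition.

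SAP 3.1 has "Full Analysis Set (FAS) Population: All patients who received a full dose of study drug", analysed as randomized. Partially dosed patients stay in the Safety Population. SAP 4.10 then states: "All efficacy analyses will be conducted using the FAS". The efficacy outputs listed in SAP 7.1 carry the Full Analysis Set label.

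SAP 5 gives the incomplete administrations as the reason, lists the change as minor, and describes it this way: "The FAS was updated to clarify that this includes only patients who received a full dose of study drug". SAP 4.2.7 says recruitment was held to "investigate six patients that did not receive complete study drug administration". Protocol 5.2.8 gives the background, that "there have been occurrences of incomplete administration of FX006 variously reported as" resistance or blockage during hip injection, and adds: "Careful review of the cases failed to identify a common factor".

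**The concern.** Neither protocol definition mentions a complete injection, so the SAP adds an exclusion rule and does not clarify an existing one. The rule depends on something that happens after randomization. Protocol 5.2.8 describes the problem only for FX006, so the exclusions probably fall mainly on the active arm. Analysing the remaining patients as randomized does not undo that selection.

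The protocol plans a per-protocol set for Part II only. In effect, the SAP gives Part I a compliance-restricted set under the Full Analysis Set name, and a reader of those tables would not expect that.

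Two uses of Part I are affected. Its data may inform whether Part II stays at 440 or could be smaller (SAP 4.1); an overstated effect would push towards a smaller, underpowered Part II. The protocol's Part II efficacy set is all treated patients, so a full-dose estimate describes a different population from the one being sized. SAP 1.2 also says the results will be used for regulatory filings, manuscripts and presentations.

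**Working it through.** **Inputs.** From SAP 4.1: about 35 patients per arm in Part I; for Part II, a difference of 0.65, SD 2.0, 90% power, two-sided alpha 0.05 and 6% early discontinuation. From SAP 4.2.7 and 5: six incomplete administrations. Part I has no stated power or SD, so the Part II SD of 2.0 is assumed for it.

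**The plan's own figure.** The normal-approximation sample size for a difference of 0.65 with SD 2.0 is 199 per arm. 199/(1 − 0.06) = 211.7, rounded up to 212, which matches the stated minimum. The 0.65 and 2.0 are therefore used as planning values below.

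**Share excluded.** 6/70 = 8.6% of Part I. If all six are FX006 patients, 6/35 = 17.1% of that arm and 0% of placebo. The arm split is not given, and Protocol 7.5.11 foresees any case in which "administration of study medication is stopped before the entire volume is injected", whichever the product. A range is therefore needed.

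**Possible bias.** Let a patients be excluded from FX006 and b from placebo. Let D be how much worse the mean Week 12 WOMAC A change of excluded patients is than that of retained patients in the same arm, taken as equal in both arms. Excluding a of 35 makes the FX006 arm look better by (a/35)D, and excluding b of 35 does the same for placebo. The overstatement of the all-treated effect is

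bias = ((a − b)/35) × D.

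The documents give no value for D, so several are shown. D = 0.65 corresponds to excluded patients losing the whole planned effect.

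| Split a/b | (a − b)/35 | D = 0.5 | D = 0.65 | D = 1 | D = 2 |
|---|---|---|---|---|---|
| 6/0 | 0.171 | 0.09 | 0.11 | 0.17 | 0.34 |
| 5/1 | 0.114 | 0.06 | 0.07 | 0.11 | 0.23 |
| 4/2 | 0.057 | 0.03 | 0.04 | 0.06 | 0.11 |
| 3/3 | 0 | 0 | 0 | 0 | 0 |

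For the 6/0 split these are 13%, 17%, 26% and 53% of the 0.65 planning difference. If excluded patients did better (D negative), or if more of them were on placebo, the signs reverse and the effect is understated.

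**Precision.** SE = 2.0 × √(1/n₁ + 1/n₂).

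- All treated, 35 v 35: SE 0.478, t-based 95% half-width 0.95.
- Six FX006 patients excluded, 29 v 35: SE 0.502, half-width 1.00.

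In the 6/0 row, bias divided by the SE of 0.502 is 0.17, 0.22, 0.34 and 0.68. The loss of precision from the exclusion is small, and sampling error exceeds every bias shown.

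**Does another analysis supply the all-treated estimate?** No. The optional sensitivity analyses in SAP 4.10.9 concern missing data and Baseline imbalance. Those in SAP 4.2.1 are for problems not known when the SAP was written, and the six cases were known.

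**The case against.** The change is declared. SAP 5 names it, gives its cause and identifies both populations affected. The stated reason is incomplete delivery, and nothing suggests that outcomes drove it. The exposure summary (SAP 4.9, Table 14.1.5) will show by arm whether the syringe was emptied, the reason if not and the volume left. Population membership will be listed by patient. Delivery was being investigated as a procedural problem, so the effect of a full dose is a sensible planning quantity. D has no source in the documents, and D = 2 is a full SD and about three times the planning effect. Part I is exploratory throughout, so correcting the SAP 5 wording and adding one all-treated WOMAC A analysis might be enough.

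Much of this stands. The exposure table will reveal the arm of the six, so the SAP need not state it. D = 2 is an extreme case; if partial delivery only forfeited the planned effect, the worst split gives 0.11 points. No confirmatory error rate is affected.

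It does not remove the point. Declaring the change as a clarification misdescribes it, and patient listings are not an estimate of the treatment effect. The full-dose quantity can be kept as a supplementary analysis without displacing the population that the protocol defines.

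**Conclusion.** The concern holds and should be fixed. The mismatch between SAP 3.1 and Protocol 9.2.1 is plain from the text, and so is the absence of any all-treated efficacy analysis. Up to six of about 70 patients are affected; the wording is up to six because the documents do not say that every case was a first injection, and one Part I patient had a second dose.

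The consequence is less certain. That the exclusions fall mainly on FX006 is an inference from Protocol 5.2.8. With no common factor found among the cases, the documents do not show whether the excluded patients' prognosis differs from that of the others. Under the assumptions of 35 per arm, SD 2.0 and D between 0.5 and 2 points, the overstatement runs from zero (3/3 split) to 0.34 points (6/0, D = 2). Randomization no longer fully protects the comparison, but the direction and size of any bias are unknown.

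**What to change.** - In SAP 3.1, define the Full Analysis Set as all randomized patients who received any study drug, full or partial, analysed as randomized, and use it for every efficacy table. Keep the existing rule for the patient who had a second dose.
- Report full-dose recipients as a separately named supplementary analysis of WOMAC A, WOMAC C and PGIC.
- In SAP 5, describe any full-dose restriction as a change to the protocol's analysis population.
- While editing, reconcile the synopsis definition with Protocol 9.2.1. The difference matters little for a model that uses only observed data, but the wording should agree.

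The cost is SAP text and one supplementary set of tables for three endpoints. No new data are needed, because these patients are already in the Safety Population. The all-treated estimate mixes full and partial delivery and may be less favourable to FX006; the supplementary analysis keeps the full-dose estimate available for planning.
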